14.1. Derivations

Duration of exposure (days) = date of last study medication – date of first study medication + 1.

15. Outcomes Variables

15.1. Primary Variable

15.1.1. Primary Variable & Derivation(s)

The primary outcome variable is the proportion of subjects completing 24 weeks adjunctive therapy during Maintenance Phase (Visit 9) defined as below.

$$\frac{\text{Number of subjects who completed up to and including the end of the Maintenance Phase (Visit 9/ EOS)}}{\text{Number of subjects in the safety population}} \times 100$$

15.1.2. Primary Analysis of Primary Outcome Variable

The primary analysis will be performed for the safety population.

The number and proportion (%) of subjects completing the 24 weeks of the Maintenance Phase will be provided along with a 95% confidence interval using the exact method.

It will be also summarized by age group, race group, gender, baseline AEDs and number of baseline AEDs.

15.2. Efficacy Variables

15.2.1. Efficacy Variables and Derivation

The following periods (days) are used in the efficacy analyses:

- Baseline: the duration (months) recorded for the number of seizure prior to screening from seizure history plus the days from screening to first dose of study medication via the paper seizure diary.
- Titration: date of Visit 3 (week 3) - Visit 2 (week 1)
- Each visit intervals between Visit 3 (week 3) and Visit 9 (week 27): Visit 3 to Visit 4, Visit 4 to Visit 5, Visit 5 to Visit 6, Visit 6 to Visit 7, Visit 7 to Visit 8, and Visit 8 to Visit 9
- First 12 weeks: date of week 15 (Visit 6)- the date of week 3 (Visit 3)
- Last 12 weeks: the date of week 27 (Visit 9 (EOS))- the date of week 15
- 24 weeks of the Maintenance Phase: date of week 27 (Visit 9 (EOS)) – date of week 3 (Visit 3)

For dropout subjects, if subject withdrew before the scheduled Visit 9(EOS), seizure data will be included for each interval up to the last date where the subject had data.

Seizure related efficacy endpoints will be derived based on the paper seizure diary data. Standard Seizure Frequency (SSF)

Seizure frequency from the subject's seizure diary data will be evaluated by standardizing the sum of seizures to a frequency per 4 weeks (28 days).

The standardized seizure frequency (SSF) for any given period (including baseline) will be calculated as:

$$\frac{\text{Total number of seizures reported in the diary during the interval of interest}}{\text{Number of days for the interval of interest}} \times 28 \text{ days}$$

The number of days on study for the interval of interest will be determined by:

Visit Date of last visit during the interval of interest - Visit Date of first visit during the interval of interest. Subject with missing paper seizure data in the interval of interest will not be counted toward the denominator.

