15.3.10. Treatment of Missing Data

Subjects who dropped out before study completion are not to be replaced and all available information obtained from them will be included in the appropriate efficacy and safety summaries to the time of dropout. No imputation is planned for any safety measures.

If the date of the seizure is missing or incomplete and the seizure cannot be allocated to a study period, these data will not be used in the analysis, but will be presented in the subject data listings. If the seizure diary was returned and there was no seizure data available for a particular day during that evaluation period, it will be assumed that the patient had missing seizure data, and the day will be excluded from the calculation of the standardized seizure frequency.

Seizure-related variables will be calculated based on available data. For dropout subjects, their seizure frequency will be derived up to the last period where the subject had data. The last period SSF will be computed based on available data prior to dropout.

16. PROCEDURE FOR CLINICAL STUDY QUALITY CONTROL, DATA COLLECTION, MANAGEMENT, AND QUALITY ASSURANCE

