3.4.2. Changes from Analyses Planned in the Protocol

Since the study drug accountability data was not collected in the data source, the number of dose taken and average daily dose will not be calculated.

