7.2. Handling of Dropouts or Missing data

Subjects who dropped out before study completion are not to be replaced and all available information obtained from them will be included in the appropriate efficacy and safety summaries to the time of dropout. No imputation is planned for any safety measures.

If the date of the seizure is missing or incomplete and the seizure cannot be allocated to a study interval, these data will not be used in the analysis, but will be presented in the subject data listings. If the seizure diary was returned and there was no seizure data available for a day during that evaluation period, it will be assumed that the patient had missing seizure data, and the day will be excluded from the calculation of the standardized seizure frequency.

Seizure related variables will be calculated based on available data. For dropout subjects, their seizure frequency will be derived for each interval up to the last interval where the subject had data. The last interval standardized seizure frequency (SSF) will be computed based on available data prior to dropout.

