15.4. Exploratory Variables

15.4.1. Analysis of Exploratory Variables

The exploratory analyses will be performed for the mITT populations.

The proportions of concordance in the daily seizure frequency during the 24-weeks of the Maintenance Phase between the watch device and paper diary as well as between the Mate application and paper seizure diary for each subject will be calculated. Proportion is calculated as the number of days with concordance in daily seizure frequency between the two Empatica devices and paper seizure diary divided by the number of days with seizure frequency available in paper diary. The mean and 95% CI (exact method) of the proportion of the concordance will be provided.

In addition, the proportion of concordance in daily seizure frequency during the 24-weeks of the Maintenance Phase between the Mate application and paper seizure diary will be calculated only with the subjects who confirmed they reported all their seizures at each day (i.e. seizure compliance='Y') in the Mate application.

SSF will be calculated for the first 12 weeks, the last 12 weeks, and the 24 weeks of the Maintenance Phase using the seizure data recorded by the investigational wearable watch device, and MATE application from Empatica.

The concordance correlation coefficient (CCC)¹ with 95% confidence interval will be calculated to assess agreement in SSF during the first 12 weeks, the last 12 weeks, and the 24 weeks of the Maintenance Phase between the two Empatica devices and the paper seizure diary.

The concordance correlation coefficient, r_c , for measuring agreement between continuous variables X and Y (both approximately normally distributed), is calculated as follows:

$$r_c = \frac{2S_{XY}}{S_{XX} + S_{YY} + (\bar{X} - \bar{Y})^2}$$

where S_{XX} = variance of X, S_{YY} = variance of Y, S_{XY} = covariance of X and Y.

This is a measure of how well a set of data (Y) compares to a “gold standard” measurement or test (X). It measures both the precision (similar to Pearson’s correlation coefficient), and accuracy (i.e. how far away results are from a 45-degree line through the origin, or from perfect concordance) of the association.

. Similar to the other correlation coefficient, the concordance correlation satisfies $-1 \leq rc \leq +1$. A value of $rc = +1$ corresponds to perfect agreement. A value of $rc = -1$ corresponds to perfect negative agreement, and a value of $rc = 0$ corresponds to no agreement.

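### SAP 15.2.1 counts seizure-frequency days as a visit-date span, while SAP 7.2 and protocol 15.3.10 leave out days without diary data; the same formula does not fit the baseline period

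*SAP*

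**What the plan says.** SAP 15.2.1 defines SSF for every period, baseline included, as a seizure count divided by a number of days and multiplied by 28. The numerator is "Total number of seizures reported in the diary during the interval of interest". The number of days is "Visit Date of last visit during the interval of interest - Visit Date of first visit during the interval of interest". The next sentence reads: "Subject with missing paper seizure data in the interval of interest will not be counted toward the denominator".

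SAP 7.2 sets the missing-data rule. It opens with "If the seizure diary was returned and there was no seizure data available for a day during that evaluation period", treats such a day as missing, and ends "the day will be excluded from the calculation of the standardized seizure frequency". Protocol 15.3.10 has the same rule, with the condition that "there was no seizure data available for a particular day during that evaluation period".

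SAP 3.4.2 lists the departures from the protocol's analyses. It mentions only that "the number of dose taken and average daily dose will not be calculated".

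For the exploratory concordance proportion, SAP 15.4.1 counts agreeing days "divided by the number of days with seizure frequency available in paper diary".

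SAP 6.3 and the first period bullet of 15.2.1 build baseline from up to three months of seizure history, at 30.42 days per month, plus the days from screening to first dose covered by the paper diary.

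**The concern.** A difference between two visit dates includes the days that SAP 7.2 and the protocol remove. Someone who programs 15.2.1 as written treats an unrecorded day as a day without seizures. Someone who programs 7.2 does not.

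The sentence after the day count does not settle this. It could refer to missing days, to subjects with any missing day, or to subjects with no data at all, and as written it removes subjects. Neither document covers a diary that was never returned, because both rules apply only to returned diaries; that is a gap and not a contradiction.

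The formula also fails for baseline if taken literally. The history part has no diary entries and no opening visit, so neither the numerator nor the visit span applies to it. The intended baseline is clear from SAP 6.3, so this is a formula to correct.

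At stake are SSF, its relative change and the 50% and 75% responder rates, all descriptive secondary endpoints, and the paper-diary SSF in the exploratory concordance coefficient. There is no control arm to offset a systematic shift.

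**Working it through.** The plan states no figure that depends on this rule, so there is nothing of its own to reproduce.

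**Inputs from the documents.** History w = 30.42, 60.84 or 91.26 days (SAP 6.3). Screening diary d = 7 to 17 days (SAP 3.1). Maintenance visits at weeks 3, 7, 11, 15, 19, 23 and 27, so 84 days for each 12-week period and 168 days for the 24 weeks. Response threshold t = 0.5.

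**Assumed.** Share of diary days without an entry m = 2%, 5%, 10% or 20%, the same in the screening diary and on treatment.

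**The two rules on one subject.** With 6 recorded seizures in 84 days, the span rule gives 28 × 6/84 = 2.00 however many days are blank. The exclusion rule gives 28 × 6/80 = 2.10 with 4 blank days and 28 × 6/70 = 2.40 with 14.

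**Case A: days missing independently of seizures.** The exclusion rule is unbiased. The span rule multiplies on-treatment SSF by (1 − m) and baseline SSF by (w + d(1 − m))/(w + d). The true reduction that just counts as a response is

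r = 1 − (1 − t)(w + d(1 − m)) / [(w + d)(1 − m)].

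At m = 10%, w = 91.26, d = 7: 1 − 0.5 × 97.56/88.434 = 0.448. At w = 30.42, d = 17: 1 − 0.5 × 45.72/42.678 = 0.464.

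**Case B: only seizure-free days skipped.** The span rule is unbiased. Under the exclusion rule

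r = 1 − (1 − t)(1 − m)(w + d) / (w + d(1 − m)).

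At m = 10% the same two settings give 1 − 0.5 × 88.434/97.56 = 0.547 and 1 − 0.5 × 42.678/45.72 = 0.533.

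True reduction that corresponds to a 50% response, as a range over 1–3 months of history and 7–17 screening days:

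| Assumed m | Case A, span rule | Case B, exclusion rule |
|---|---|---|
| 2% | 49.1–49.3% | 50.6–50.9% |
| 5% | 47.6–48.3% | 51.6–52.3% |
| 10% | 44.8–46.4% | 53.3–54.7% |
| 20% | 38.4–42.0% | 56.9–59.4% |

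**Which rule is nearer the truth on treatment.** Let f be the share of on-treatment seizures that fall on unrecorded days. The span rule multiplies SSF by 1 − f and the exclusion rule by (1 − f)/(1 − m). For f below m the absolute errors are f and (m − f)/(1 − m), which are equal at f = m/(2 − m): 0.05/1.95 = 2.6% at m = 5%, and 0.10/1.90 = 5.3% at m = 10%. Above that value, about half the proportionate share, the exclusion rule is nearer.

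**Case C: one unreturned diary (the gap).** Assume one diary of a nominal 28 days is lost, the subject stays in the analysis, seizures are spread evenly and the other diaries are complete. The span rule multiplies SSF by 56/84 = 2/3 for a 12-week period and 140/168 = 5/6 for the 24 weeks. The true reduction that counts as a 50% response is 1 − 0.5/(2/3) = 25% and 1 − 0.5/(5/6) = 40%.

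**The case against.** The strongest reply is that the two sections can be read together: 15.2.1 gives the general interval length and 7.2, which names this very quantity, takes out the missing days. The sentence after the day count may be a garbled restatement of that rule, since the denominator of SSF is days and a subject cannot be counted in it. This is a fair guess at the intent. But no text gives 7.2 precedence, 15.2.1 is the operative derivation, and 15.4.1 shows that the SAP says days available when it means them.

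Several points on that side stand:

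- Missing days may be few. Protocol 11.2.2.4 requires a daily entry and staff review at visits, and exclusion criterion 24 removes subjects judged unable to keep diaries. At 2–5% missing, the 50% threshold moves by only about 0.6 to 2.4 percentage points. Nothing in the documents supports the 10% and 20% rows over the others.
- The direction of bias depends on why days are missing.
- The large figures in case C measure the unreturned-diary gap and not the contradiction. One reading of 15.2.1 would drop such a subject.
- The baseline point is a correction of wording only.
- Dividing by recorded days, with no minimum, can give a 28-day rate from very few days.

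**Conclusion.** The concern holds. Followed literally, SAP 15.2.1 contradicts SAP 7.2 and protocol 15.3.10, and the SAP does not declare the change. The rules differ only when diary days are missing. Under the span rule on-treatment SSF is correct if no seizure fell on an unrecorded day and otherwise too low. Under the exclusion rule it is correct if days are missing independently of seizures and too high if mainly seizure-free days are skipped.

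The size rests on the assumed missing-day rate: a shift of a point or two in the effective 50% threshold at low rates, and several points at 10% or more. The number of subjects affected is unknown. Days after dropout are already handled in 15.2.1. Primary retention, the seizure-free proportion and time on ESL do not use this day count. The matter should be fixed before the analysis, but it does not threaten the primary result.

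**What to change.** In SAP 15.2.1:

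- Define the denominator as the number of days in the interval with a paper-diary entry, Yes or No. State that this also covers unreturned diaries, which goes beyond 7.2.
- Replace the sentence on subjects with missing data: days without an entry are not counted, and a subject with no paper-diary data in an interval has no SSF for it.
- Report the visit-span version as a sensitivity analysis, with the percentage of days without an entry by arm and interval. That table will also show whether any rates rest on very few days.
- Give baseline its own formula: (history seizures + screening-diary seizures) / (30.42 × months of history + screening days with an entry) × 28.

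If the span rule is what is meant, list it in 3.4.2 and correct 7.2.

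A minor addition for the same edit: 15.2.1.2 divides by baseline SSF and no rule covers a value of 0, which inclusion criteria 5 and 6 make unlikely but do not exclude. State that relative change is then not calculated, report how many such subjects there are, and say how they are classed in the responder rates.

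The cost is SAP wording, programming and one sensitivity table. The diary in protocol Appendix III already asks for Yes or No each day, and 15.4.1 already needs the count of available days in the Maintenance Phase. Reported reductions may be slightly smaller than under the span rule. If skipped days are mainly seizure-free, the new rule will understate the reduction, and the sensitivity analysis would show this.

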15.2.1.2. Relative Reduction in SSF

Seizure frequency change from the baseline period will be evaluated by using SSF per 4 weeks (28 days).

The relative (%) change from baseline in SSF is calculated as:

$$\frac{\text{SSF for the interval of interest} - \text{SSF at baseline}}{\text{SSF at baseline}} \times 100$$

Further the relative change from baseline will be categorized into:

- 100% Decrease
- $\geq 75\% - < 100\%$ Decrease

- $\geq 50\% - < 75\%$ Decrease
- 0% to $< 50\%$ Decrease
- $> 0\% \text{ to } < 25\%$ Increase
- $\geq 25\% \text{ to } < 50\%$ increase
- $\geq 50\% \text{ to } < 100\%$ increase
- $\geq 100\%$ increase

15.2.1.3. Responder Rates

50% and 75% responder rate ($\geq 50\%$ and $\geq 75\%$ reduction from baseline in SSF) will be calculated for the intervals of interest. The proportion will be calculated as the number of responders divided by the total number of subjects in the modified ITT population entering the period of interest.

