3.3. Determination of Sample Size

Sample size is determined outside of statistical consideration. Approximately 100 subjects will be enrolled, almost evenly split between Arm 1 (first add-on) and Arm 2 (later add-on). Assuming the completion rates at 24 weeks of the Maintenance Phase are 60% and 50% for Arm 1 and Arm 2 respectively, the width of 95% CI for completion rate will be approximately 14% based on normal approximation method.

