15.2.1.4. Proportion of Seizure-Free Subjects

Subjects who did not have any seizure as per the paper seizure diary for the intervals of interest will be deemed seizure free, for the corresponding interval of interest. Subjects must complete each interval of interest without any seizures to be considered seizure-free for each interval of interest. Subject with no seizure data available during interval of interest will not be considered seizure-free for the interval of interest. However, subjects who discontinue prior to Visit 9 will be considered not seizure-free for the interval when the discontinuation takes place and all subsequent intervals (even if the subjects are seizure-free at the time of discontinuation). Anyone who drops out from the study and does not complete the 24 weeks (Visit 9), is included in the denominator for the proportion.

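### Responder rates divide by subjects entering each period while seizure-free rates keep dropouts, so later responder rates depend on who leaves and cannot be read across periods or against seizure freedom

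*SAP*

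**What the plan says.** For the 50% and 75% responder rates, SAP 15.2.1.3 sets the base as "the total number of subjects in the modified ITT population entering the period of interest". Which subjects enter a period follows from the period definitions in SAP 15.2.1. The late period, for example, is given as "Last 12 weeks: the date of week 27 (Visit 9 (EOS))- the date of week 15", so it starts at Visit 6.

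For seizure freedom, SAP 15.2.1.4 treats a subject who discontinues as "considered not seizure-free for the interval when the discontinuation takes place and all subsequent intervals", and adds: "Anyone who drops out from the study and does not complete the 24 weeks (Visit 9), is included in the denominator for the proportion".

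Three other provisions bear on the point:

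- SAP 7.2, on a dropout's final interval: "The last interval standardized seizure frequency (SSF) will be computed based on available data prior to dropout". A subject who leaves during a period can therefore still count as a responder on partial data.
- SAP 15.2.1, in the seizure frequency derivation: "Subject with missing paper seizure data in the interval of interest will not be counted toward the denominator". If this is also meant to govern responder rates, the base shrinks further. The SAP does not say.
- Protocol 15.2 and 15.3.6 assign efficacy analyses to the mITT population and define the two response thresholds. They give no period-specific denominator.

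Neither document plans a responder rate on a fixed denominator, or one with discontinued subjects counted as non-responders.

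**The concern.** The study expects heavy attrition. SAP 3.3 reads: "Assuming the completion rates at 24 weeks of the Maintenance Phase are 60% and 50% for Arm 1 and Arm 2 respectively". Protocol 7.3.4 says that both efficacy and tolerability influence whether subjects stay, and Protocol 13 lists lack of efficacy among the discontinuation reasons. Response and dropout may therefore be related.

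There is no comparator and no hypothesis test, so a reader will judge seizure control from the raw percentages and their course over time. With a base that changes from period to period, part of that course can reflect who has left. In a table that sets the last-12-week responder rate beside the last-12-week seizure-free rate, the first would describe subjects who reached Visit 6 and the second would also carry those who had gone. A reader could not tell this from the percentages.

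**Working it through.** **Who is in each denominator**

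| Period | Responder rate (15.2.1.3) | Seizure-free rate (15.2.1.4) |
|---|---|---|
| First 12 weeks (from Visit 3) | mITT subjects reaching Visit 3 | dropouts kept as failures |
| Full 24 weeks (from Visit 3) | mITT subjects reaching Visit 3 | dropouts kept as failures |
| Last 12 weeks (from Visit 6) | only those reaching Visit 6 | dropouts kept as failures |
| Visit 8 to Visit 9 | only those reaching Visit 8 | dropouts kept as failures |

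The first two responder denominators lose only titration dropouts. The last two lose everyone who left earlier.

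**Inputs**

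- Completion c: 0.60 (Arm 1) and 0.50 (Arm 2), from SAP 3.3.
- Subjects per arm: 50, from SAP 3.1. The protocol plans 93 and 97. The percentages below do not depend on this number when responders are a fixed share of it.
- Time from first dose: 2 weeks to Visit 3, 14 to Visit 6, 22 to Visit 8, 26 to Visit 9.
- Responders: 20 of 50, with a range of 15 to 25. **This is an assumption**; the documents give no responder rate.
- Dropout pattern: constant hazard over 26 weeks, also an assumption.

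**The plan's own figure.** No responder figure is stated. The one figure resting on these inputs is the 14% precision in SAP 3.3. 1.96 × √(0.6 × 0.4 / 50) = 13.6 points and 1.96 × √(0.5 × 0.5 / 50) = 13.9 points, so it reproduces as a half-width.

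**Subjects remaining**, 50 × c^(t/26):

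| | Visit 3 | Visit 6 | Visit 8 |
|---|---|---|---|
| Arm 1 | 50 × 0.6^(2/26) = 48.07 | 50 × 0.6^(14/26) = 37.98 | 50 × 0.6^(22/26) = 32.45 |
| Arm 2 | 50 × 0.5^(2/26) = 47.40 | 50 × 0.5^(14/26) = 34.43 | 50 × 0.5^(22/26) = 27.81 |

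**Case 1: all leavers are non-responders, and nobody's seizure control changes**

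| | Last 12 weeks, planned rule | Visit 8 to 9, planned rule | Of those reaching Visit 3 | Of all 50 |
|---|---|---|---|---|
| Arm 1 | 20/37.98 = 52.7% | 20/32.45 = 61.6% | 20/48.07 = 41.6% | 40% |
| Arm 2 | 20/34.43 = 58.1% | 20/27.81 = 71.9% | 20/47.40 = 42.2% | 40% |

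For the last 12 weeks the gap from the Visit 3 base is 52.7 − 41.6 = 11.1 points in Arm 1 and 58.1 − 42.2 = 15.9 points in Arm 2. It scales with the assumed number of responders:

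- 15 responders: 39.5% against 31.2% (Arm 1) and 43.6% against 31.6% (Arm 2).
- 25 responders: 65.8% against 52.0% (Arm 1) and 72.6% against 52.7% (Arm 2).

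With uniform dropout the fractions left at Visit 6 are 0.785 and 0.731, and 20 responders give 20/39.2 = 51.0% and 20/36.5 = 54.7%.

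**Case 2: dropout unrelated to response.** If 40% of any group respond, the planned last-12-week rate is (0.40 × 37.98)/37.98 = 40% in Arm 1, and likewise 40% in Arm 2. It does not move. A rate that counts every discontinued subject as a non-responder leaves 0.40 × 30 = 12 and 0.40 × 25 = 10 responders among completers, or 12/50 = 24% and 10/50 = 20%.

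**Case 3: all leavers before Visit 6 are responders.** The planned rate falls to (20 − 12.02)/37.98 = 21.0% in Arm 1 and (20 − 15.57)/34.43 = 12.9% in Arm 2.

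**The case against.** A reader might infer that attrition alone pushes later responder rates up. The documents do not support that. Case 2 shows no movement and Case 3 a fall. Protocol 13 lists adverse events, withdrawal by subject, pregnancy and other exit reasons besides lack of efficacy, and Protocol 7.3.4 names tolerability as a driver of retention. The direction is unknown in advance.

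A reader might also infer that the fixed-denominator rate is the correct one and should replace the planned rate. It has the mirror-image weakness: in Case 2 it reports 24% and 20% when 40% of any group respond. Since retention is the primary endpoint, it also folds part of that outcome into the responder rate. Which rate leads is a choice of estimand.

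Further points in the plan's favour:

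- The denominator is stated openly.
- Using available data up to dropout is in Protocol 15.3.10.
- Attrition is visible in the retention rate, the disposition table and the Kaplan-Meier analysis of time on ESL.
- No test or arm comparison rests on the responder rate.
- The first-12-week and 24-week denominators are nearly unaffected.

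All of this stands, and it argues against replacing the planned rate. It does not answer the mismatch. The available-data rule governs how a subject's seizure frequency is derived and does not require the responder base to shrink. The SAP already keeps dropouts for seizure freedom.

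**Conclusion.** The point holds in a limited form. SAP 15.2.1.3 and 15.2.1.4 use different bases for the same periods. Responder rates for the last 12 weeks and later visit intervals describe successively smaller groups, so they should not be compared across periods or with the seizure-free rate. That much follows from the text, whichever way any bias runs.

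The size is conditional. If all leavers are non-responders, the last-12-week rate under the stated assumptions is about 53% and 58%, against about 42% of subjects reaching Visit 3 (40% of all 50). If dropout is unrelated to response, the trend in the planned rate is not distorted. This is a reporting improvement worth making before database lock; it does not invalidate the planned rate.

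**What to change.** In SAP 15.2.1.3, for every Maintenance period:

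- Add a responder rate on the same denominator as 15.2.1.4, counting a subject who discontinues as a non-responder in the interval of discontinuation and in all later ones.
- State, for both endpoints, whether subjects who left during titration are in the denominator.
- Keep the planned rate beside it, labelled as subjects still on study, and print n for each period.
- State whether the missing-diary rule in 15.2.1 applies to the responder denominators.

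In SAP 15.2.2.3, add the first 12, last 12 and full 24 weeks. SAP 2.4.2 names them as responder endpoints, but the output list stops at baseline, titration and the visit intervals. SAP 15.2.2.5 has the same gap for seizure freedom.

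The cost is a few SAP sentences and additional table lines, with no new data. The added rate will be lower than the planned one, and conservative when dropout is unrelated to response, which is why both should be shown.
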